## 4 Study Design and Endpoints

### 4.1 Description of Study Design

This multi-center, double-blind, placebo-controlled, randomized Phase 2/3 trial will study the safety, tolerability, and efficacy of bardoxolone methyl in patients hospitalized with confirmed COVID-19. Phase 2 is designed to provide an early interim analysis for safety and will enroll approximately 40 patients. Phase 3 is designed to determine whether bardoxolone methyl increases the probability of recovery at Day 29 compared with matching placebo. In phase 3, approximately 360-400 additional patients will be enrolled.

Patients will be randomized using permuted block randomization in a 1:1 fashion to either once-daily administration of bardoxolone methyl (20 mg) or matching placebo. Randomization will be stratified by study center and invasive mechanical ventilation (i.e., mechanical ventilation with endotracheal intubation) use at baseline (yes or no).

Enrollment of patients  $\geq 70$  years of age may be limited (e.g., comprise no more than 10% of all randomized patients), pending safety review by the DSMB and executive committee. Treatment will be administered for the duration of hospitalization (until recovery), with an expected duration of 10 days. For patients who are still hospitalized for more than 10 days, treatment can be continued for a maximum treatment duration of 29 days. Dose de-escalation (down to 10 mg) is permitted during the study if indicated clinically, and subsequent dose re-escalation is also permitted. Once a patient's dose has been reduced, dose re-escalation back to a higher dose is permitted.

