Randomization will be performed using an interactive web response system (IWRS). Following randomization on Day 1, patients will be assessed while hospitalized on Days 3, 5, 8, 11, 15, 22, and 29. Assessments will include clinical status assessments, vital sign measurements, clinical chemistry collection, and adverse event collection. Patients that recover prior to Day 29 will complete an end-of-treatment visit. Patients will have an in-person follow-up on Day 29, regardless of treatment adherence and recovery status prior to Day 29, and a safety follow-up 60 days after randomization for clinical status assessments, vital sign measurements, clinical chemistry collection, and adverse event collection. Follow-up in-person visits are preferred but recognizing quarantine and other factors may limit the subject's ability to return to the site for the visit. In this case, the visit may be performed by phone. An independent Data and Safety Monitoring Board (DSMB) will advise the study leadership on safety aspects and overall progress of the study.

The phase 2 primary endpoint will be assessed during the treatment phase, defined as while hospitalized and up to Day 15. The phase 3 primary endpoint will be assessed during the treatment phase, defined as while hospitalized and up to Day 29. Enrollment of the phase 3 cohort will initiate after safety and proof of concept has been confirmed in the Phase 2 cohort.

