### **6.1.9 Duration of Therapy**

Patients will receive study drug while hospitalized (until recovery) with an expected duration of 10 days. For patients who are still hospitalized for more than 10 days, treatment can be continued for a maximum treatment duration of 29 days.

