#### **7.2.2.9 End of Treatment Visit (or Day of Recovery if prior to Day 29)**

- Due to the nature of this visit (end of treatment or day of recovery), study drug will not be administered at this visit.
- Verify study drug was administered in accordance with [Section 6](#) of protocol since the last visit.
- Review and record concurrent medications.
- Review and record available laboratory assessments as indicated in [Table 1](#).
- Review and record vital signs, results of medical examinations, results of laboratory assessment, and other assessments as indicated in [Table 1](#).
- Assess clinical status.
- Assess recovery status.
- Record adverse events as reported by participant or observed by investigator.

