#### **10.4.4.1 Adverse Events**

The Medical Dictionary for Regulatory Activities (MedDRA) dictionary will be used to classify all AEs reported during the study by system organ class (SOC) and preferred term (PT). All summary tables will include counts of patients with treatment-emergent adverse events (TEAEs). TEAEs are defined as those AEs that have an onset time either at or after the start of study drug administration and no more than 30 days after the last dose of study drug is administered. An overall summary of TEAEs will be presented with the number and percentage of patients having a TEAE, a serious TEAE, a TEAE leading to study discontinuation, a TEAE with an outcome of death, a TEAE related to study drug (definitely, probably, or possibly related), or a severe TEAE. The overall incidence of TEAEs will be summarized by SOC and by SOC and PT using the number and percentage of patients reporting an event and the number of events reported. The incidence of serious TEAEs and TEAEs leading to premature study discontinuation will be summarized in a similar manner. TEAEs will also be summarized by maximum severity (mild, moderate, or severe), and assessed relationship to study drug with the percentage of patients in each category. TEAEs leading to premature study discontinuation, and TEAEs with an outcome of death will also be presented in separate listings.

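### The adverse event counting window closes 30 days after the last dose and dosing stops at recovery, so events starting after about Day 31 are counted unequally, by a modest amount and in an uncertain direction between arms

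*Combined protocol and SAP*

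**What the plan says.** **Counting rule.** Section 10.4.4.1 builds all adverse event summary tables on treatment-emergent events (TEAEs). The window opens at first dose ("TEAEs are defined as those AEs that have an onset time either at or after the start of study drug administration") and closes "no more than 30 days after the last dose of study drug is administered". The tables give numbers and percentages of patients and numbers of events. No person-time or exposure adjustment is stated.

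**Dosing.** Section 6.1.9: "Patients will receive study drug while hospitalized (until recovery) with an expected duration of 10 days". For longer stays, Section 4.1 says "treatment can be continued for a maximum treatment duration of 29 days". At the end-of-treatment or recovery visit (Section 7.2.2.9), "study drug will not be administered at this visit". Section 10.4.5 summarizes treatment duration by arm, separately from the event counts.

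**Follow-up.** This is tied to randomization, not to last dose. Section 4.1 schedules a Day 29 visit for everyone and "a safety follow-up 60 days after randomization for clinical status assessments, vital sign measurements, clinical chemistry collection, and adverse event collection". Section 5.7.1 keeps patients who stop drug in the study.

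**What is collected.** Three places disagree:
- Section 8.3 captures all adverse events, from consent until 7 days (non-serious) or 30 days (serious) after the end of participation.
- Section 8.4.1 takes serious events from first dose to the final visit but does not report those related to COVID-19.
- A footnote to the schedule of assessments (Section 19) restricts collection to serious events with a reasonable possibility of being drug-related.

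**The concern.** The length of the counting window is set by when a patient recovers, stops drug or dies. These are post-randomization outcomes, and the trial is designed to change the first of them. If the arms differ in dosing duration, crude percentages compare unequal periods of observation, and some difference can appear with identical event rates. Assessing safety against placebo is a Phase 3 primary objective (Section 3.2.1), so readers will compare these tables across arms.

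The second consequence concerns late fatal events. If a patient stops drug early and a fatal event starts more than 30 days after the last dose, it is not a TEAE. Its onset is after Day 31, so the death is also too late for the Day 29 mortality endpoint (Section 4.2.2.2).

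**Working it through.** **1. Inputs.** Section 10.4.4.1: window end = last-dose day + 30. Sections 4.1 and 19: first dose on Day 1, at most 29 days of treatment. Section 10.5: recovery 50% on placebo and 64% on bardoxolone methyl, 400 patients, 2% dropout. No figure in the plan is disputed here. The recovery rates belong to a sample size that reproduces: 196 per arm gives 392, and 392/0.98 = 400, with 80.2% power at 196 per arm. The expected number recovered also agrees (200 × 0.50 + 200 × 0.64 = 228).

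**2. Window by last dose (surviving patients).**

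| Last dose | Window closes | Days short of Day 60 |
|---|---|---|
| Day 1 | Day 31 | 29 |
| Day 5 | Day 35 | 25 |
| Day 10 | Day 40 | 20 |
| Day 15 | Day 45 | 15 |
| Day 22 | Day 52 | 8 |
| Day 29 | Day 59 | 1 |

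The spread is 59 − 31 = 28 days. No window closes before Day 31.

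**3. Mean window by arm, no deaths.** Assume recovered patients have their last dose on Day L and all others on Day 29. Mean window = p(L + 30) + (1 − p) × 59, where p is the recovery proportion.
- L = 5: placebo 0.50 × 35 + 0.50 × 59 = 47.0; bardoxolone methyl 0.64 × 35 + 0.36 × 59 = 43.6; difference 3.4 days (7.1%).
- L = 10: 49.5 and 46.8; difference 2.7 days (5.4%).
- L = 15: 52.0 and 50.0; difference 2.0 days (3.8%).

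If no dose is given on Day 29 because the end-of-treatment visit falls then, 59 becomes 58 and each difference falls by 0.14 × 1 = 0.14 days.

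**4. Adding deaths.** Take L = 10 and assume a share s of non-recovered patients die, on Day 15 on average, with observation ending at death. The non-recovered mean is 15s + 59(1 − s). Placebo minus bardoxolone methyl is 0.14 × (that mean − 40).
- s = 0: +2.7 days (shorter on bardoxolone methyl)
- s = 0.3: +0.8 days
- s = 0.6: −1.0 day (longer on bardoxolone methyl)
- s = 1: −3.5 days

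The sign changes at s = (59 − 40)/(59 − 15) = 19/44 = 0.43.

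**5. Effect on percentages (illustrative).** Assume equal hazards in both arms and no deaths. With a constant hazard of 0.1 to 1.0 events per 30 days and L = 5 to 15, the window alone lowers the bardoxolone methyl TEAE percentage by about 0.5 to 2.6 points. A constant hazard probably overstates late events. For L = 10, the difference is 0.14 × (risk by Day 59 − risk by Day 40):
- Constant 2% per day: 0.14 × [(1 − e^−1.18) − (1 − e^−0.80)] = 0.14 × (0.693 − 0.551) = 2.0 points.
- 2% per day to Day 29, then 0.2% per day: 0.14 × [(1 − e^−0.640) − (1 − e^−0.602)] = 0.14 × (0.473 − 0.452) = 0.3 points.

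All hazards are assumptions; the documents give none.

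**The case against.** **The first month is intact.** This stands. A reader might infer that the Phase 2 Day 29 safety endpoint is cut short. It is not, because the shortest window closes on Day 31. Section 2.4.1 also places fluid overload in the first three to four weeks and transaminase peaks at two to four weeks. Only muscle spasm is described as extending to two months.

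**The direction is not shown.** This stands. A reader might infer that a drug which speeds recovery must look safer. Step 4 shows that deaths can reverse the sign.

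**Late deaths are largely captured.** This stands in part. The rule works on onset, so a fatal event starting inside the window counts even if death follows later. It would be too strong to say that early stoppers' deaths after Day 29 are lost in general. Unexpected deaths are a safety endpoint without this window (Section 3.2.3), and Day 60 recovery requires being alive (Section 4.2.2.3). However, Section 8.2.3 lists death among expected COVID-19 events, and the recovery composite does not report deaths separately.

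**A fixed-period measure exists.** Section 8.4.1 asks for cumulative incidence to the final visit. It sits under IRB reporting and covers only serious, unexpected, possibly related events.

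**The analysis is descriptive, and detail is deferred to the formal SAP.** This is true (Sections 10.1, 10.4 and 10.4.4), and treatment duration by arm would show unequal exposure. The formal SAP is not in the supplied text and could add a fixed-window table. The text that is supplied defines the window, applies it to every summary table and promises no alternative.

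**Conclusion.** The point holds in a limited form. The TEAE window depends on a post-randomization outcome, closes between Day 31 and Day 59 for survivors, and feeds unadjusted by-arm percentages. The unequal counting affects only onsets after about Day 31, including fatal events starting more than 30 days after the last dose.

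Under the plan's recovery rates, the mean window is 2.0 to 3.4 days (about 4% to 7%) shorter on bardoxolone methyl. This assumes last dose on Day 5 to 15 if recovered, Day 29 otherwise, and no deaths. The assumption also equates recovery at Day 29 with early stopping of drug, which is a simplification. With enough deaths among the non-recovered the difference reverses. The documents support neither a predictable bias in favour of the drug nor a large one.

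A reader might also assume that all adverse events are on file for everyone to Day 60. The visits are scheduled, but Sections 8.3, 8.4.1 and 19 conflict on what is recorded. Alive status, at least, is part of the Day 60 recovery assessment.

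**What to change.** 1. Pre-specify in the SAP, before unblinding, a by-arm summary of serious events, deaths and whatever adverse events are collected. Use a fixed window from first dose through Day 60 for everyone in the safety population, whatever the date of last dose. Present it alongside the last dose + 30 days TEAE tables. A separate Day 29 table would recover no events lost to the present rule.
2. Reconcile Section 8.3, Section 8.4.1 and the schedule footnote in Section 19 on which events are collected and for how long, so that the Day 60 table has one consistent source.

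The fixed window adds 1 day of counting for a patient last dosed on Day 29, 20 days for Day 10 and 29 days for a single dose. It removes the dependence on dosing duration, although death still ends time at risk. It needs no new visits. The cost is a few tables and more off-treatment events in the summary, which is why the TEAE tables should stay beside it.

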##### 4.2.1.1 Primary Endpoint

- Safety (e.g., frequency, intensity, and relationship to study drug of serious adverse events [including unexpected deaths], change from baseline in vital sign and laboratory assessments) at Day 29

CONFIDENTIAL

This material is the property of the NYU School of Medicine and Langone Medical Center. Do not disclose or use except as authorized in writing by the study sponsor

## 4.2.2 Phase 3

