### 8.2.2 Relationship to Study Agent

For all collected AEs, the clinician who examines and evaluates the participant will determine the AE's causality based on temporal relationship and his/her clinical judgment. The degree of certainty about causality will be graded using the categories below.

- **Definitely Related** – The event follows: (a) a reasonable, temporal sequence from study drug or a study procedure; and (b) cannot be explained by the known characteristics of the participant's clinical state or other therapies; and (c) evaluation of the participant's clinical state indicates to the investigator that the experience is definitely related to study procedures.
- **Probably Related** – The event should be assessed following the same criteria for "Definitely Related". If in the investigator's opinion at least one or more of the criteria are not present, then it can be assessed as "probably" related.
- **Possibly Related** – The event should be assessed following the same criteria for "Definitely Related". If in the investigator's opinion at least one or more of the criteria are not present, then it can be assessed as "possibly" related.
- **Probably Not Related** – The event occurred while the participant was receiving study drug/intervention or undergoing study procedures but can reasonably be explained by the known characteristics of the participant's clinical state or other therapies.
- **Definitely Not Related** – The event is definitely produced by the participant's clinical state or by other therapies administered to the participant.
- **Uncertain Relationship**: The event does not meet any of the criteria previously outlined.

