### 8.3 Time Period and Frequency for Event Assessment and Follow-Up

The occurrence of an AE or SAE may come to the attention of study personnel during study visits and interviews of a study participant presenting for medical care, or upon review by a study monitor. All adverse events will be captured on the appropriate eCRF. Information to be collected includes event description, time of onset, clinician's assessment of severity, relationship to study product (assessed only by those with the training and authority to make a diagnosis), and time of resolution/stabilization of the event. All AEs will be followed to adequate resolution.

Any medical condition that is present at the time that the participant is screened will be considered as baseline and not reported as an AE. However, if the study participant's condition deteriorates at any time during the study, it will be recorded as an AE. UPs will be recorded in the data collection system throughout the study.

Changes in the severity of an AE will be documented to allow an assessment of the duration of the event at each level of severity to be performed. AEs characterized as intermittent require documentation of onset and duration of each episode.

The PI will record all reportable events with start dates occurring any time after informed consent is obtained until 7 (for non-serious AEs) or 30 days (for SAEs) after the last day of study participation. At each study visit, the investigator will inquire about the occurrence of AE/SAEs since the last visit. Events will be followed for outcome information until resolution or stabilization.

CONFIDENTIAL

This material is the property of the NYU School of Medicine and Langone Medical Center. Do not disclose or use except as authorized in writing by the study sponsor

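### The related-TEAE count in Section 10.4.4.1 leaves out the Uncertain Relationship grade, so its headline row omits events whose link to study drug was not ruled out

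*Combined protocol and SAP*

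**What the plan says.** Section 8.2.2 has the examining clinician grade every collected adverse event as definitely, probably or possibly related, probably not or definitely not related, or of uncertain relationship. The last is a residual grade: "The event does not meet any of the criteria previously outlined".

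Section 10.4.4.1 lists the rows of the overall TEAE summary, ending with "a TEAE related to study drug (definitely, probably, or possibly related), or a severe TEAE". The bracket is a closed list of three grades. The same section also says:

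- TEAEs will be tabulated by "assessed relationship to study drug with the percentage of patients in each category".
- "The overall incidence of TEAEs will be summarized by SOC and by SOC and PT", with no restriction by causality. Serious TEAEs are to be summarized in a similar way.

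The Phase 2 primary endpoint in Section 4.2.1.1 includes the "relationship to study drug of serious adverse events", next to their frequency and intensity and to changes in vital signs and laboratory values.

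**The concern.** A row labelled as TEAEs related to study drug is usually read as every event for which a drug link remains open. Here it is narrower. An event that the investigator could place under none of the five attributed grades drops out of the row and leaves no trace in it.

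Attribution will often be difficult in this population. Section 2.4.1.2 reports transaminase rises in almost all patients given the drug. Section 8.2.3 lists marked liver-test elevation and acute kidney injury among the events expected from COVID-19 itself. A residual grade may therefore be used, and the handling of unresolved causality should be a deliberate choice. For a safety summary the cautious choice is to count it and show the narrower figure beside it.

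The relationship of serious events to study drug is also named in the Phase 2 primary endpoint, where each arm has only about 20 patients.

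**Working it through.** This is a comparison of texts. The plan states no figure to reproduce.

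**Step 1: map the grades (Section 8.2.2) to the outputs (Section 10.4.4.1).**

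| Grade | Pooled related row | By-category table | All-cause, serious, fatal rows |
|---|---|---|---|
| Definitely related | yes | yes | yes |
| Probably related | yes | yes | yes |
| Possibly related | yes | yes | yes |
| Probably not related | no | yes | yes |
| Definitely not related | no | yes | yes |
| Uncertain relationship | no | yes | yes |

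Three of the six grades feed the row and three do not. No not-related row is defined.

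**Step 2: what has an Uncertain event failed to meet?** By definition, all the earlier criteria. That includes Probably Not Related, which needs a reasonable explanation from clinical state or other therapies, and Definitely Not Related, where "The event is definitely produced by the participant's clinical state or by other therapies administered to the participant". It has met no related definition either. It is neither ruled in nor ruled out, yet it falls outside the row together with the two grades that carry a positive alternative explanation.

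**Step 3: can the reader rebuild the wider count from the by-category table?** Not reliably. A patient may have events of several grades. If patients appear once in each grade they have, adding the Uncertain line to the pooled row counts some of them twice. If they appear once at their strongest grade, the plan gives no rank for Uncertain. The table is also specified for TEAEs in general. No relationship count for serious TEAEs is stated.

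**Step 4: size.** Let *u* be the share of patients in an arm whose only event not ruled out as related is graded Uncertain. Including the grade raises that arm's row by *u*.

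- Phase 2: about 40 patients randomized 1:1 gives about 20 per arm. One such patient adds 1/20 = 5 percentage points.
- Full trial: about 200 per arm (Section 10.5). The documents give no value for *u*, so the following are assumptions. *u* = 0 adds 0 patients; *u* = 5% adds 0.05 × 200 = 10; *u* = 10% adds 0.10 × 200 = 20.
- Between arms: the difference in the row changes by *u* (bardoxolone) minus *u* (placebo). If the grade is used equally in both arms, the difference does not change.

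**The case against.** The strongest reply is that the row is one of several, and that nothing is hidden. The by-category table gives Uncertain its own line. All, serious, severe and fatal TEAEs are counted whatever the causality grade, so a serious event graded Uncertain still appears as a serious TEAE. All of this stands, and it is why the point is minor.

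The second reply is that the grade may hardly be used. Probably and Possibly Related share the same wording, under which, if "at least one or more of the criteria are not present, then it can be assessed as" probably or possibly related, either grade is open. Most doubtful events could go there and be counted. This stands as a limit on size. It does not change what the rule does with an event that is graded Uncertain. One route to the grade is plain: Probably Not Related is worded for events during dosing or study procedures, while TEAEs run to 30 days after the last dose. That route cuts both ways, because such an event may have an ordinary clinical explanation.

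The third reply is that Section 10.4 offers brief descriptions and leaves detail to the formal SAP. The pooling rule, however, is already written. Section 10.1 requires the SAP only before database lock and unblinding, so it need not be settled before the Phase 2 safety review.

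A reader might infer that the plan scores Uncertain events as not related, that drug-related harm is undercounted, or that the decision to open Phase 3 is biased. The documents do not support this. Absence from one row does not assign an event to its opposite. An Uncertain event has not been shown to be drug-related. The endpoint in Section 4.2.1.1 prescribes no pooled count. Section 10.4.7.1 has the DSMB review unblinded data under its charter, and no section makes this row a criterion for proceeding.

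One adjacent conflict could make the matter moot. Section 8.3 says "All adverse events will be captured on the appropriate eCRF", while a footnote to the Schedule of Assessments restricts collection to serious events with a reasonable possibility of relationship. If the footnote governs, Uncertain events might not reach the database.

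**Conclusion.** The related-TEAE row omits one of the six causality grades, and events with that grade have not been ruled out as related. The omission follows from a stated closed list. The effect is confined to that row and to anything that quotes it; the causality-free counts are untouched.

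The size cannot be derived from the documents. It could be zero, it is 5 percentage points per affected patient in a Phase 2 arm, and the range of 0 to 20 patients per arm in the full trial rests entirely on the assumed 0% to 10%. The conclusion also assumes that Uncertain events are collected, which depends on how the conflict between Section 8.3 and the schedule footnote is resolved. Severity: minor.

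**What to change.** In Section 10.4.4.1, and in the formal SAP, make these changes:

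1. Extend the bracket to *(definitely, probably, possibly related, or uncertain relationship)*.
2. Show beside it the count without Uncertain, with each patient counted once in each version, so that both readings are available by arm.
3. Add the same pair of counts for serious TEAEs, since none is now specified and relationship of serious events belongs to the Phase 2 primary endpoint. Use them in the Phase 2 DSMB tables too.
4. Keep the by-category table.

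Separately, reconcile Section 8.3 with the collection footnote in the Schedule of Assessments, so that it is clear whether events of uncertain relationship are recorded.

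The wording and programming cost is one line of text and one derivation flag, plus the added serious-event rows. The drawback is that the wider related count may rise slightly in both arms and will mix some unclassifiable events with attributed ones. The narrower count shown beside it lets the reader see how much.

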#### **5.7 Participant Treatment Discontinuation**

##### **5.7.1 Reasons for Treatment Discontinuation**

Study drug discontinuation refers to a patient's stopping administration of study drug. Participants are free to discontinue study treatment at any time for any reason without prejudice to their medical care. Furthermore, the investigator may discontinue a patient from study drug. The reason for a patient's discontinuation from study drug will be recorded in the electronic case report form (eCRF).

Reasons for study drug discontinuation may include the following:

- Adverse event;
- Death;
- Lost to follow-up;
- Physician decision;
- Protocol specified criterion met;
- Withdrawal by subject

Patients who are discontinued from study drug should still continue in the study, complete all study visits, and undergo all scheduled study assessments, if possible.

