#### **5.8 Participant Withdrawal or Termination**

##### **5.8.1 Reasons for Withdrawal or Termination**

Participants are free to withdraw from participation in the study at any time upon request, without prejudice to their medical care. The reason for a patient's withdrawal or termination will be recorded in an electronic case report form (eCRF). The potential reasons could be:

CONFIDENTIAL

This material is the property of the NYU School of Medicine and Langone Medical Center. Do not disclose or use except as authorized in writing by the study sponsor

- Withdrawal of Consent by Participant
- Lost to Follow-up

Discontinuation of treatment is not a withdrawal of participation from the study. If treatment is discontinued, the participant should remain in the study and continue to be assessed at the scheduled study assessments.

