#### **8.1.1 Definition of Adverse Events (AE)**

An **adverse event** (AE) is any symptom, sign, illness or experience that develops or worsens in severity during the course of the study. Intercurrent illnesses or injuries should be regarded as adverse events. Abnormal results of diagnostic procedures are considered to be adverse events if the abnormality:

CONFIDENTIAL

This material is the property of the NYU School of Medicine and Langone Medical Center. Do not disclose or use except as authorized in writing by the study sponsor

- results in study withdrawal
- is associated with a serious adverse event
- is associated with clinical signs or symptoms
- leads to additional treatment or to further diagnostic tests
- is considered by the investigator to be of clinical significance

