## 8.2 Classification of an Adverse Event

### 8.2.1 Severity of Event

Severity for each adverse event will be graded using the NCI Common Terminology Criteria for Adverse Events (CTCAE) system. All adverse events will be recorded:

- Grade 1: Mild; asymptomatic or mild symptoms; clinical or diagnostic observations only; intervention not indicated.
- Grade 2: Moderate; minimal, local or noninvasive intervention indicated; limiting age-appropriate instrumental activities of daily living.
- Grade 3: Severe or medically significant but not immediately life-threatening; hospitalization or prolongation of hospitalization indicated; disabling; limiting self care activities of daily living.
- Grade 4: Life-threatening consequences; urgent intervention indicated.
- Grade 5: Death related to AE.

CONFIDENTIAL

This material is the property of the NYU School of Medicine and Langone Medical Center. Do not disclose or use except as authorized in writing by the study sponsor

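### The AE outputs count events leading to study discontinuation, so patients who stop drug for an AE but stay in follow-up are in none of them

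*Combined protocol and SAP*

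**What the plan says.** Section 10.4.4.1 uses leaving the study as its category in three outputs:

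- Overall summary: "a TEAE leading to study discontinuation, a TEAE with an outcome of death" are among the lines.
- Table by system organ class (SOC) and preferred term (PT): "The incidence of serious TEAEs and TEAEs leading to premature study discontinuation will be summarized in a similar manner".
- Listing: "TEAEs leading to premature study discontinuation, and TEAEs with an outcome of death will also be presented in separate listings".

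Section 5.7.1 treats stopping drug as a separate event. Under "Reasons for study drug discontinuation may include the following", the first item is adverse event. The reason goes on the eCRF, and the patient is to remain in the study and complete its visits where possible. Section 5.8.1 states the separation outright: "Discontinuation of treatment is not a withdrawal of participation from the study". The reasons it gives for leaving the study are consent withdrawal and loss to follow-up, presented as possibilities and not as a closed list.

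On severity, section 8.2.1 records CTCAE Grades 1 to 5, including "Grade 4: Life-threatening consequences; urgent intervention indicated". Section 10.4.4.1 plans three levels: "TEAEs will also be summarized by maximum severity (mild, moderate, or severe".

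On collection, section 8.3 says that every AE is captured on the eCRF. A footnote to the schedule of assessments in section 19 limits collection to AEs that are serious and possibly drug-related.

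**The concern.** Tolerability is one of the trial's stated aims (Protocol Summary; section 4.1), and section 10.4.4 evaluates it partly through AEs. A count of patients whose drug was stopped because of an AE is a basic tolerability result. As the plan defines its terms, an AE would mostly lead to stopping drug, and a patient who then stays for Day 29 and Day 60 follows the protocol. That patient has not left the study, so the category used in section 10.4.4.1 does not apply. The better sites keep such patients in follow-up, the fewer of them the outputs show. A reader of the tables could take a low count as good tolerability when it reflects good retention.

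Two neighbouring points affect the same outputs. Grade 4 has no stated place in a three-level severity table. And if the schedule footnote governs, a non-serious AE that stops drug may never be collected, so no relabelled table could show it.

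**Working it through.** **1. The texts side by side**

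| Question | Section | Answer |
|---|---|---|
| Is an AE a listed reason for stopping drug? | 5.7.1 | Yes, first in the list |
| Does that patient leave the study? | 5.7.1, 5.8.1 | No |
| Is an AE a listed reason for leaving the study? | 5.8.1 | No, but the list is illustrative |
| Which event do the three AE outputs count? | 10.4.4.1 | Leaving the study |
| Does another planned summary count drug stops caused by an AE? | 10.4.5 | No: completed or discontinued counts and treatment duration only |

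**2. The plan's own figure, to confirm the arm size and dropout inputs (section 10.5)**

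Inputs: recovery 50% vs 64%, two-sided 0.05, 80% power, 1:1 allocation, 2% dropout. Mean proportion = (0.50 + 0.64)/2 = 0.57.

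n per arm = [1.96 × √(2 × 0.57 × 0.43) + 0.8416 × √(0.50 × 0.50 + 0.64 × 0.36)]² / 0.14² = (1.372 + 0.583)² / 0.0196 ≈ 195.1, rounded up to 196.

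Total = 392; 392 / 0.98 = 400. Power at 196 per arm is 80.2%. The plan's figure reproduces, so 200 per arm and 2% dropout are sound inputs.

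**3. How full the outputs would be on the literal wording**

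Expected dropouts per arm = 200 × 0.02 = 4. In a Phase 2 arm of 20 it is 20 × 0.02 = 0.4. Let s be the share of dropouts caused by an AE. The documents do not give s, so a range is shown. Expected count = 200 × 0.02 × s; chance of a zero count in the arm = (1 − 0.02s)^200.

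| s (assumed) | Expected per 200 | Chance of zero |
|---|---|---|
| 100% | 4 | 2% |
| 50% | 2 | 13% |
| 25% | 1 | 37% |
| 10% | 0.4 | 67% |

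**4. What a drug-discontinuation table would hold**

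The documents give no rate of drug stops for an AE. Expected count = 200 × assumed rate.

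| Assumed rate | Per 200-patient arm |
|---|---|
| 2% | 4 |
| 5% | 10 |
| 10% | 20 |
| 15% | 30 |

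At 2% the count equals the all-cause dropout figure, but the patients are different: one group left the study, the other stopped drug.

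**5. Whether the data needed are collected**

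- The drug-stop reason is on the eCRF (5.7.1), but it is a reason for the patient. It does not identify the AE responsible, which an SOC/PT table and a listing need.
- The AE fields named in 8.3 are description, onset, severity, relationship and resolution. None records what was done with study drug.
- Reasons for dose reduction are to be documented (6.1.8), but the section does not say on the eCRF. No section says that reasons for interruption are collected.

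**The case against.** The strongest reply is that study discontinuation is loose wording for study drug discontinuation, in which case the outputs would be populated. The documents do not rule this out. But the same paragraph writes study drug in full when it means the drug, and a programmer could derive the flag from either disposition record. The wording needs settling on either reading.

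A reader might infer that the outputs must be empty. The documents do not support that. The list in 5.8.1 is open, a participant may withdraw consent because of an AE, and section 8.1.1 foresees an abnormality that "results in study withdrawal". A reader might also infer that many drug stops will be hidden. No document rate supports a number. Section 2.4.1.2 reports transaminase elevations above 3 times ULN in about 4% to 11% of patients, but describes them as generally self-limiting on continued treatment, so that is not a drug-stop rate.

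It is tempting to extend the point to the AE definition in 8.1.1, whose first criterion names study withdrawal and not stopping drug. That goes too far: the criteria are alternatives, and an abnormality serious enough to stop drug would ordinarily qualify as clinically significant in the investigator's view. Nor is death missing from the severity reporting, since fatal TEAEs have their own summary line and listing. Events with immediate risk to life are SAEs under 8.1.2 and appear in the serious tables. What remains is that Grade 4 is not assigned to a level.

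It is also fair that patients who stop drug still appear under any, related, serious or severe TEAEs as applicable, that 10.4.5 reports treatment duration by arm, and that 10.1 makes a separate SAP the final arbiter. Those points limit the damage. None of them counts AE-caused drug stops, and section 10.4.4.1 as written would lead the SAP to repeat the same category.

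**Conclusion.** The mismatch is real and worth correcting. Followed as written, the three outputs miss patients who stop drug for an AE and stay in follow-up, and no other planned summary counts them. The outputs would probably be sparse: at most about 4 expected per 200-patient arm if every planned dropout were AE-caused, against about 4 to 30 per arm for assumed drug-stop rates of 2% to 15%.

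This rests on the literal reading of 10.4.4.1, on the 2% dropout assumption, and on rates that the documents do not supply. The 2% covers the period to Day 29 and not to Day 60. The plan does not say whether a fatal TEAE counts as leading to study discontinuation; if it does, the counts would be higher but would reflect deaths, not tolerability. The primary endpoint, alpha and sample size are not touched.

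**What to change.** 1. In 10.4.4.1, use TEAEs leading to study drug discontinuation in the overall summary, the SOC/PT table and the listing. Report TEAEs leading to study withdrawal separately, and say where fatal events are counted.
2. Add an action-taken-with-study-drug field to the AE form, so that each stop is linked to the AE that caused it. Summarize dose reduction and interruption where they are recorded.
3. Tabulate maximum severity by CTCAE grade as recorded under 8.2.1, which gives Grade 4 its own row.
4. Reconcile the AE footnote in the schedule of assessments with section 8.3. Without this, non-serious AEs that stop drug may not reach the database.

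The cost is small: one added AE field and minor programming. It is more than a wording change, because items 2 and 4 concern data collection and should be settled while AEs are still being recorded. Items 1 and 3 can be fixed in the SAP before database lock.
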